Hypothesis 1c: The Specific Mechanisms Model hypothesizes that if changes in content, process, and activity level are mechanisms specific to CT, MM, and AS, respectively, then treatment condition will have a significant effect on early changes in the mechanism variables (i.e., the effects of the three treatments on the three mechanism variables will be different, with CT having the largest effects on early treatment decreases in catastrophizing, MM having the largest effects on early treatment increases in non-judgment, and AS having the largest effects on early treatment increases in activity level). Further, later improvement in the primary outcome will be predicted by different mechanism variables as a function of treatment condition; that is, late treatment changes in pain interference will be substantially and uniquely predicted by early treatment changes in: (1) cognitive content (i.e., pain catastrophizing) in CT but not in MM or AS; (2) cognitive process (i.e., non-judgment) in MM but not in CT or AS; and (3) activity level in AS but not in CT or MM, in addition to each mechanism variable significantly predicting the primary outcome (Specific Mechanisms Model).

We also predict that change in the mechanism variables will precede and predict change in outcome, but not vice versa.

A2b. Secondary Aim and Hypotheses

Aim 2: Evaluate the post-treatment mechanisms that explain relapse, maintenance, and continued gains.

As a secondary aim, this study will also evaluate the post-treatment mechanisms that explain relapse, maintenance, and continued gains associated with these treatments [**Aim 2; Secondary**]. The Shared (Hypothesis 2a) and Specific (Hypothesis 2b) Mechanisms Models will also be applied to data collected via EMA and ActiGraph daily during the 4-weeks post-treatment to better understand the post-treatment mechanisms that underlie maintenance of gains and relapse.

Hypothesis 2a: Early post-treatment changes (i.e., post-treatment to 2-weeks post-treatment) in cognitive content, cognitive process, and activity level will be significantly associated with late post-treatment changes (i.e., 2-weeks post-treatment to 4-weeks post-treatment) in pain interference.

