B.1.5. Selecting the mechanisms to study should be grounded in theory. Various psychosocial treatments have different theoretical bases that propose unique cognitive, behavioral, and emotional therapeutic processes from which treatment-specific mechanisms are derived. In regards to the treatment-specific mechanisms of psychosocial therapies (including CT, MM, and AS), [name] recently proposed a theoretical model that made a distinction between cognitive content (i.e., what patients believe about their pain), cognitive processes (i.e., how patients think about their pain), and behavioral mechanisms (i.e., what people do).¹¹ Theoretically, CT targets change in maladaptive cognitive content (i.e., pain catastrophizing) and this is purported to be critical to improve pain outcomes.²² Hence, change in what patients think is theorized to be a mechanism specific to CT. In contrast, MM explicitly targets change in cognitive processes (i.e., non-judgmental awareness), and this is thought to underlie improved pain outcomes. AS is based on operant theory and is designed to target what patients do in response to pain, specifically to extinguish maladaptive pain behaviors, and to reinforce engagement in goal-directed well behaviors. However, minimal research has examined whether these treatments engender benefit via these specific theorized pathways – the Specific Mechanisms Model – or if benefit is obtained via an amalgamation of shared pathways – the Shared Mechanisms Model. Thus, the question as to whether it is more important to target change in cognitive content, cognitive processes, or behavior, or equally important to focus on all three of these factors, is not yet known.

Tentative support for CT theory exists with several investigations of correlations among pre-to post-treatment change scores finding that improvements in cognitive content variables such as pain catastrophizing,^{e.g.,23-26} pain control beliefs,^{20-24,25,27} pain helplessness,²⁸ and other pain-related beliefs²³ are associated with improved outcomes. Further, prospective macro-level (i.e.,

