At the end of the study when it comes time to conduct data analysis, study investigators (including those unblinded to intervention, such as both co-PIs) may need access to the data, in order to conduct specific analyses. Since (1) no investigators would be able to link any individual participant whose name was heard in fidelity recordings to any study data, and (2) any data investigators (blinded or unblinded) have access to at this point in the project would be locked, it is thus possible for unblinded investigators to also partake in data analysis.

Any staff member listed above may, with discretion from the co-PIs, participate in the actual writing/editing portion of any manuscript(s) that result from this study. During the data collection

phase of the study, blinded staff will not analyze or report data. Once the data is locked, all staff members, unblinded or blinded, may assist with analyzing or reporting data as needed.

D6s. Statistical Analyses

Structural equation modeling (SEM) will be used to evaluate the extent to which early treatment changes in catastrophizing, activity level, and non-judgment predict subsequent late treatment changes in pain interference, and the extent to which these associations are shared across the three treatments, or if some are unique to a subset of the treatments (Aim 1). We will also use SEM to examine the mechanisms of maintenance of gains from post-treatment to follow-up, to address the secondary study aim. Relevant covariates will be tested for and appropriately controlled for (when indicated) across all models. The Hochberg and Benjamini procedure will be used to control for alpha inflation in all analyses. This alpha control procedure involves putting the significance levels of the planned primary analyses in ascending order, and matching them to the actual significance levels obtained with the analyses, also placed in ascending order.

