Figure 3 below represents the initial model we plan to test for the catastrophizing mechanism variable, providing that it evidences at least a small effect for change for at least one treatment condition during the first two weeks of treatment. However, the model will be simplified (by removing treatment condition as a predictor, and the paths associated with treatment condition) if non-significant treatment effects are found. Up to two additional SEM models will also be tested, with non-judgment and activity level as the foci. Below we describe the specific steps planned to address the study aims and test the primary study hypotheses.

Figure 3. Initial model testing the mechanism role of pain catastrophizing during treatment

Step 1. Ensure at least small time effects (slope) in the early mechanism variables for at least one of the treatment conditions (a requirement for that variable to be considered as a possible mechanism).

- (1) We will perform an initial one-way Analysis of Variance (ANOVA) comparing the pre- to mid-treatment mechanism slopes between the three treatment conditions, separately for each of the three mechanism variables, with a goal of identifying the effect (i.e., Eta squared, η^2) associated with any between group differences in early changes in mechanism variable. If this effect size is < 0.01 , this would indicate a less than small between-group difference in the amount of early treatment change for that mechanism;

this would be interpreted to mean that all three treatment conditions had a similar effect on early treatment change in the mechanism variable.

- (2) In the event that a less than small between condition effect is found, we would then examine the pre- to mid-treatment time effect of this mechanism collapsed across groups to see if this mechanism changes from pre- to mid-treatment (i.e., early treatment). If this effect size (η^2) associated with this time effect collapsed across groups for any mechanism variable is less than 0.01 (representing a small time effect) then there would be evidence that the variable in question is unlikely to act as a mechanism, because at least some change over time early in treatment for that variable, on average, is needed for it to serve as a mechanism.

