- (3) If less than small effects emerge for both the between-group effects on the early mechanism slope *and* for the time effect (i.e., average slope), this would be interpreted to indicate a lack of early change (in any treatment condition) on the mechanism variable. In this instance, that mechanism variable would not be tested in a subsequent SEM. If *either* of the effect sizes are equal to or larger than 0.01 (indicating a small or larger time effect, on average) or a small or large Group X Time effect emerges (indicating at least a small group effect on early change in mechanism), then we will proceed to Step 2 for that mechanism variable.

Step 2. Test the model presented in Figure 3 for any mechanism variable that met the Step 1 conditions described above.

- (4) First paths a_1 and a_2 will be tested. The a_1 and a_2 coefficients represent the strength of the predictive relationships from the two dummy IVs¹ to early treatment slope in catastrophizing (i.e., to evaluate the impact of treatment condition on early treatment changes in catastrophizing). Together, these tell us if treatment condition had a direct effect on the early treatment slope in the mechanism variables. If both of these coefficients are non-significant (consistent with the Shared Mechanisms Model) they will be eliminated from the final SEM. If either or both of these pathways are statistically significant, this will be interpreted to mean that there is a between-treatment condition difference in early change in the mechanism variable being evaluated, and these effects will be retained in the model.
- (5) In the case of at least one statistically significant a coefficient, we will perform planned post-hoc ANOVA models for each of the three treatment groups to understand these differences and to determine if the findings are consistent with the Specific Mechanisms Model. For example, if catastrophizing is uniquely targeted by CT, we would anticipate a significant treatment condition effect (in either or both of the two a coefficients) on early catastrophizing slope, with post hoc tests indicating larger pre- to mid-treatment decreases in catastrophizing for the CT condition than the MM or AS interventions. However, the full test of the Specific Mechanisms Model also takes into account the b path, described below.

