¹ In the proposed SEM, treatment condition (i.e., which of three treatments the participant is assigned to) is represented by two variables: "CTvsOther" (coded as "1" if the participant is assigned to the CT condition, "0" if not) and "MMvsOther" (coded as "1" if the participant is assigned to the MM condition, "0" if not). These two dummy variables are exogenous and have a correlation of $r = .50$ (if groups are of equal size). When considered in the same model (i.e., when controlling for the other), the two variables contain information about all three treatment conditions.

[figure not shown]
(6) In order to establish a mechanism effect on outcome (i.e., that cognitive content, cognitive process, or activity level predicts subsequent change in pain interference) we will next test for significance of the *b* coefficients. We will test the *b* coefficient for significance across each of the three mechanism variables (i.e., three significance tests, one per SEM model). Any *b* coefficients that are not significant indicate that early change in that mechanism variable is not associated with late change in pain interference, indicating a lack of support for it as a mechanism variable in treatment. A significant *b* coefficient will be interpreted as evidence supporting early treatment change in the mechanism variable in question as explaining late treatment change in pain interference.

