As indicated, up to three SEMs (one for each mechanism) will evaluate and test for significance of the *a* and *b* coefficients for each mechanism variable that met the Step 1 assumptions described above (i.e., that evidenced at least a small early slope or larger, for at least one of the treatments). The combination of a treatment effect on the mechanism variable (coefficient *a*) and a significant *b* coefficient for a particular mechanism variable (indicating that early change in the mechanism variable predicts a late change in outcome), with *post hoc* tests linking each treatment to its targeted mechanism variable (i.e., CT, MM, and AS having the largest effects on cognitive content, cognitive process, and activity level, respectively) would support the Specific Mechanisms Model. A significant *b* coefficient in light of non-significant *a* coefficients (i.e., the mechanism plays a role in outcome, but all three treatments have a similar impact on the mechanism variable) would support a Shared Mechanisms Model. Thus, together, the significance levels of the *a* and *b* coefficients will address the study aims. In short, the results of the (maximum) six planned statistical tests (i.e., whether or not there are between-group differences in the three early mechanism slopes, and the significance level of the three *b* coefficients) will allow us to evaluate if the three mechanism variables play a role in treatment outcome, and whether this role is shared between the treatments or unique to a subset of them.

Exploratory Moderation Analyses

We also plan to conduct a preliminary test of the LAE model. Specifically, SEM will be used to evaluate the extent to which baseline catastrophizing, activity levels, and non-judgment are respectively associated with response to CT, AS, and MM. Figure 4 below illustrates the statistical approach that we propose to use to evaluate the LAE model. For illustrative purposes, only the role of baseline catastrophizing moderating response to treatment is depicted. As per the above models, the treatment condition variable is represented by two variables: "CTvsOther" (coded as "1" if the participant is assigned to the CT condition, "0" if not) and "MMvsOther" (coded as "1" if the participant is assigned to the MM condition, "0" if not). When considered in the same model (i.e., when controlling for the other), the two variables contain information about all three treatment conditions.

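### Each mechanism's b path is tested without adjusting for the other two mechanisms, so a significant b cannot by itself show that the mechanism explains late change in pain interference

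*Combined protocol and SAP*

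**What the plan says.** D6s sets out a model for catastrophizing (Figure 3) and then states: "Up to two additional SEM models will also be tested, with non-judgment and activity level as the foci". The b paths are tested as "three significance tests, one per SEM model", and the summary after item (6) repeats that "up to three SEMs (one for each mechanism) will evaluate and test for significance of the" a and b coefficients. A significant b is taken as evidence supporting "early treatment change in the mechanism variable in question as explaining late treatment change in pain interference". Three of the six primary tests are these b's.

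Two provisions bear on adjustment. The opening of D6s says "Relevant covariates will be tested for and appropriately controlled for (when indicated) across all models", without naming the other mechanisms; the only covariate listed in Table 3 is whether low back pain is the primary or a secondary problem. Step 1 is a screen: if both the between-group effect and the overall time effect fall below an eta-squared of 0.01, "that mechanism variable would not be tested in a subsequent SEM".

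The decision rules differ by model. A Specific Mechanisms conclusion needs a treatment effect on the mechanism (path a), a significant b, and post hoc tests matching each treatment to its target. A Shared Mechanisms conclusion needs only a significant b with non-significant a paths.

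**The concern.** A b from a model with one mechanism measures that mechanism's association with late pain interference, including whatever it carries for the mechanisms left out. If early changes in catastrophizing, non-judgment and activity run together within persons, a bystander has a genuine marginal association with outcome. The multiplicity procedure does not remove it, because that association is not a chance finding.

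The protocol gives some reason to expect overlap. The moderation hypotheses in A2c expect each treatment to act indirectly on the mechanisms that the others target, and D6u cites falls in catastrophizing under all three treatments. The background (B.1.5) asks "whether it is more important to target change in cognitive content, cognitive processes, or behavior", which single-mechanism b's cannot answer. At stake is the primary aim: a variable could be reported as a shared mechanism of all three treatments only because it tracks another one.

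**Working it through.** **Inputs from the documents.** N = 240 analysed (D5: 300 × 0.80 = 240); medium effect r = 0.30 for path b, power 0.80, and six alpha levels from 0.050 to 0.008 (D6u, Table 5). For sensitivity, r = 0.57 between change in catastrophizing and change in pain interference (D6u). That figure is for pre-to-post changes over the same period, so for a lagged effect it is a high value.

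**Assumed.** The correlation ρ between early mechanism slopes, equal for all pairs, from 0.2 to 0.7. Two-sided tests. No treatment effect on the mechanisms.

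**The plan's own figures first.** For the mediation rows of Table 5, requiring power(a) × power(b) ≥ 0.80 gives 107, 126 and 137 with noncentral t, and 111, 131 and 142 with Fisher z, against 109, 129 and 140 printed. For the interaction rows, f² = 0.15 with 2 numerator degrees of freedom gives exactly 93, 98 and 102. Table 5 therefore reproduces. It contains no correlation between mechanisms.

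**Marginal signal of a mechanism with no direct effect.** If only mechanism 1 acts, with standardised effect b, mechanism 2 has correlation r₂ = ρb with the outcome. At ρ = 0.5 and b = 0.30, r₂ = 0.15. The noncentrality is 0.15 × √240 / √(1 − 0.15²) = 2.35, which gives a rejection probability of 65% at 0.05 and 38% at 0.008.

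**Under step-up testing over six tests.** Simulation: one true mechanism, two with no direct effect, three null a-path tests. One-at-a-time regressions were compared with one regression holding all three slopes. The first column uses false-discovery-rate thresholds, 0.05 × i/6. The second uses the thresholds printed in Table 5, which equal 0.05/k for k = 1 to 6. The plan's name for the procedure allows either.

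| ρ (b = 0.30) | Declared alone, 0.05 × i/6 | Declared alone, 0.05/k | Power for true mechanism, joint model |
|---|---|---|---|
| 0.2 | 8% | 5% | 97% |
| 0.3 | 18% | 12% | 97% |
| 0.5 | 52% | 42% | 90% |
| 0.6 | 70% | 61% | 83% |
| 0.7 | 84% | 78% | 69% |

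The declared rates are per mechanism with no direct effect; repeat runs differ by one or two points. In the joint model that rate is about 2% (first thresholds) or 1% (second) at every ρ. Single-mechanism power for the true mechanism is about 98%. With b = 0.57 and the first thresholds, the one-at-a-time rates are 28–29% at ρ = 0.2, 64–65% at 0.3 and 99% at 0.5.

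**Check on the joint-model power.** With three equally correlated predictors the variance inflation is 1/(1 − 2ρ²/(1 + ρ)): 1.16, 1.50, 1.82 and 2.36 at ρ = 0.3, 0.5, 0.6 and 0.7. The noncentrality is 0.30 × √240 / √(0.91 × inflation) = 4.52, 3.98, 3.61 and 3.17. Against a critical value of about 2.66 (two-sided 0.05/6), power is about 97%, 91%, 83% and 70%, in line with the simulation.

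**Early pain-interference slope.** If Figure 3 also adjusts for it, the one-at-a-time rates at a fixed 0.05 change from 28%, 65% and 81% to 24%, 58% and 74% at ρ = 0.3, 0.5 and 0.6 (early outcome slope driven 0.30 by the true mechanism). The problem remains.

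**The case against.** The other side has strong points, and several limit the conclusion.

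- **The word *uniquely*.** A reader might infer that Hypothesis 1c promises mutually adjusted effects, since "late treatment changes in pain interference will be substantially and uniquely predicted by early treatment changes in" the targeted mechanism. The sentence goes on to contrast treatments (each mechanism in one treatment but not in the other two), and D6s uses *unique* in the same sense. Testing that claim needs a treatment-by-mechanism comparison of b, which a joint model does not supply. This point does not rest on the word.
- **Hypothesis 1a asks only for association.** A single-mechanism b tests that directly, and a real marginal association is not an error there. This stands, and is why those models should remain.
- **No direct effect does not mean no role.** If non-judgment acts through catastrophizing, it shows the same correlations as a bystander, and adjusting for catastrophizing would hide a real upstream mechanism. This stands. It argues against replacing the single-mechanism b's with adjusted ones as the primary tests.
- **The correlation is not documented.** A2c and D6u speak mainly of average treatment effects, which do not establish correlation between persons. Activity is measured by actigraphy and the other two by self-report, so one common ρ of 0.5 or more may be too high. A reader might infer that a bystander will be declared; the documents support only that it can be.
- **A false Specific conclusion is harder to reach.** It also needs a significant a path and matching post hoc tests, neither of which is simulated here.
- **Existing safeguards.** The covariate sentence is generic, and Step 1 screens for early change; neither adjusts for the other mechanisms. The Figure 3 diagram was not available for this check, but the text defines it as the catastrophizing model.
- **Which mechanism to target first** is otherwise left to exploratory time-series analyses. That is fair for ranking, but it does not cure the explanatory reading of b in Step 2.

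**Conclusion.** The gap is real but conditional. Step 2 gives an explanatory reading to coefficients that are unadjusted for the other two mechanisms, and no written model supplies the adjustment. At N = 240 and b = 0.30, a mechanism with no direct effect can be declared in about 8%, 18%, 52% and 84% of trials at slope correlations of 0.2, 0.3, 0.5 and 0.7, against about 2% in a joint model. On the Table 5 thresholds the figures are 5%, 12%, 42% and 78%, against about 1%. At low correlations the excess is modest; near-certainty needs a high correlation or a much larger b. The figures assume equal correlations, normal slopes, simple regressions in place of the full three-wave model, and that the variable passes Step 1.

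The exposure falls mainly on the Shared Mechanisms conclusion, which a significant b with non-significant a paths is enough to trigger. The documents do not support saying that the tests of Hypothesis 1a are invalid, or that the single-mechanism b's must lose their primary status.

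**What to change.** In D6s, Step 2:

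- Keep the three single-mechanism models as the test of association for Hypothesis 1a.
- Prespecify one parallel-mechanism model in which all early mechanism slopes that pass Step 1 are correlated predictors of the late pain-interference slope, with the treatment dummies leading to each mechanism.
- Report adjusted b's with confidence intervals beside the unadjusted ones, and state the level at which adjusted b's are judged. The power figures above assume the same six-test step-up.
- State that a mechanism is said to explain late change independently of the others only if its adjusted b supports it. Otherwise describe the single-model b as an association unadjusted for the other mechanisms, which may be indirect.
- Report the observed correlations among the early slopes, so that readers can judge how much the two sets of b's could differ.

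The cost is SAP wording and one further model, with no new data. The statistical price is precision: from about 98%, power for the true mechanism falls to about 97%, 90%, 83% and 69% at correlations of 0.3, 0.5, 0.6 and 0.7. It is therefore below the planned 80% at 0.7, where a non-significant adjusted b should not be read as evidence against a mechanism.
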